9.4 Circulating DNA Assessment

Despite the relative paucity of RS cells in the tumor, the detection of cell free circulating tumor DNA (ctDNA) is feasible in cHL. A number of next generation sequencing (NGS)-based ctDNA detection methodologies have been studied in cHL. NGS-based ctDNA detection performed by NGS of the immunoglobulin (Ig) genes can identify ctDNA in the peripheral blood mononuclear cells (PBMC) and plasma (cell-free ctDNA) at diagnosis in 73% of patients with cHL. Using a separate NGS method, Vandenberghe and colleagues identified cHL-specific genomic imbalances in ctDNA at diagnosis that became undetectable after treatment. In another study using digital droplet PCR, XPO1 mutations were detected at diagnosis in cHL patients and the persistence of this mutation in patients with a negative PET scan at the end of treatment showed a possible association with relapse. Most recently, using a panel-directed NGS-based approach, noninvasive genotyping of cHL was validated in cHL (feasible in 87.5% of patients evaluated) and enabled monitoring of clonal evolution in patients with patients with treatment failure. Most notably, the presence and rate of ctDNA decline with standard treatment as well as with nivolumab treatment was found to be highly associated with the presence of active lymphoma and with PFS. This latter, panel-directed NGS method has the greatest potential for being the most sensitive and specific tool for ctDNA detection in cHL. The validation of ctDNA in cHL, as a sensitive and specific marker of the eradication of the malignant clone, has the potential to supplant PET-CT scans as a dynamic disease assessment tool. Dynamic response to therapy and the detection of residual cHL are suboptimal with PET scans, which are the current gold standard. There remain a high number of disease progression events in patients who have negative interim and end of treatment PET scans. Furthermore, interpreting PET scans remains particularly challenging in the setting of PD-1 inhibition, even requiring a modification to the standard lymphoma response assessment criteria (i.e. LYRIC criteria). We propose to evaluate the ability of ctDNA assessment to detect 9p24.1 molecular abnormalities, a known prognostic/predictive marker that would be advantageous to detect using a non-invasive method due to the labor intensive methods required for FISH. In addition, in order to determine the most sensitive and specific measure of cHL eradication, we will compare detection of ctDNA at interim and end of treatment time points to PET-CT results to reliably identify disease progression events. This analysis will be carried out in collaboration with [name] at the Dana Farber Cancer Institute.

9.5 Quantitative PET Assessment in Hodgkin Lymphoma

For better characterization of therapeutic response and prediction of outcome in patients with lymphoma, significant progress has been made in standardizing qualitative methods and integration of FDG PET in the international working group criteria (IWG) for lymphoma assessment¹⁶. However, there is a growing need for the development of quantitative imaging metrics as operator-independent surrogate measures to predict treatment response and survival. In this regard, standardized uptake values (SUV) have been the most widely used quantitative measure for assessing tumor metabolic activity and treatment response. In Hodgkin lymphoma (HL), SUV_{max} cut-off was investigated as a predictor of progression after two cycles of chemotherapy⁷⁷, however, without validation studies to define a widely accepted cut off value, these criteria have not yet been adopted for HL.

The PET-derived whole body metabolic metrics, metabolically active tumor volume (MTV*) and total lesion glycolysis (TLG**) measure metabolic activity in an entire tumor mass to reflect tumor biology. With the recent development of software based automated assessments, volume-based metabolic parameters have become increasingly available quantitative PET (qPET) indices. Although, these metrics have the potential to become a useful index for assessing treatment response and survival they are yet to be standardized and validated to translate to a clinical practice platform. Recent studies have reported that a high total MTV predicted a lower survival in various retrospective studies in HL showing variation in the strength of outcome prediction but promising data in early stage HL⁷⁸⁻⁸². Based on these encouraging

results, there is interest in utilizing qPET parameters, including MTV, to tailor treatment in HL, but these metrics require validation in larger, prospective studies. In addition, there is controversy with respect to the methodologies used among various investigators^{78,79,83}, though studies that have evaluated different methodologies have shown similar utility to the various methods⁸⁴. Preliminary results suggest that qPET metrics may not be applicable across treatment regimens. As part of the HD18 trial by the German Hodgkin Lymphoma Study Group Mettler et al found that baseline MTV was a predictive factor for early response to BEACOPP after two cycles. However, no prognostic value for end of treatment response and ultimate outcome was observed with an interim PET-adapted treatment strategy⁸³. However, in the LYSA AHL2011 trial, which utilized a similar PET-adapted BEACOPP-based approach in advanced stage HL, MTV was prognostic for PFS. When combined with interim PET status, MTV and interim PET results together identified a subset of patients at high risk for treatment failure⁸⁵.

In patients with relapsed or refractory HL treated with sequential BV followed by ICE chemotherapy (in patients not in complete response after BV), baseline MTV and TLG were found to be strong prognostic factors for outcome. In multivariate analyses, baseline MTV remained the main independently prognostic factor associated with treatment outcome along with end of treatment PET status, and baseline MTV enhanced the prognostic value of end of treatment PET status for outcome⁸⁶. Thus, there are data to support the use of qPET parameters as a prognostic factor in HL, both alone and in combination with the dynamic response data gained with interim or end of treatment PET.

The intention of this work is to validate the prognostic value of qPET metrics, in particular MTV, in a prospective trial incorporating novel immunotherapy into the treatment of relapsed/refractory HL.

*MTV measure the total volume, hence measured in cm³ or ml, of the metabolically active tumor volume encompassed by a VOI, both for a single lesion and for multiple lesions.

**TLG is the product of SUVmean in the defined VOI and the MTV; the rationale is to combine tumor burden and its metabolic activity, having an index that is correlated to the volume and the uptake of the volume.

9.5.1 Methods of qPET parameters:

PET/CT scans were performed after 6–8 hours of fasting and after the intravenous administration of ~10–15 mCi (370–555 MBq) of 18F-FDG. After 50–70 minutes of radiotracer uptake, PET images were acquired on a non-contrast 16-slice PET/CT system (GE Medical Systems). Three-dimensional (3D) iterative reconstruction using a 168 × 168 matrix with a zoom of 1.0, FWHM filter of either 5.0 or 6.0 mm, and 2 iterations with 8 subsets was used generate PET images. The non-contrast whole body CT data was utilized for lesion anatomic localization and attenuation correction. 18F-FDG PET/CT images region-of-interest (ROI) will be performed using the commercially available, FDA-approved “Mirada Medical PET/CT XD Oncology Review” software (Mirada Medical) and SECTRATM. The ROI measurement - Standard uptake value (SUV; g/mL) – attempts to measure the normalized amount of radioactive concentration found on qualitative (visual) PET inspection in selected part of the body at a certain time. Some variation of the normalization factor for the SUV exist, including: body weight (SUVbw), lean body weight (SUVlbw), and body surface area (SUVbsa). Calculations reported in this study will rely on the general standard of care: SUVbw and it is calculated using the formula recommended by the QIBA SUV Subcommittee:

SUVbw(pixel) in g/mL = activity (pixel) in (Bq/ml)/injected dose in Bq/patient weight in grams).

Image DICOM tags are used to perform the calculation, including: patient's weight, acquisition date time, radionuclide half-life and radiopharmaceutical start date/time.

The background red marrow of each patient was defined by using a 1 cm³ diameter region of interest in the most inferior vertebral body which did not demonstrate focally increased FDG uptake or vertebroplasty material. Focal lesions for each patient were defined as focal areas, measuring at least 1 cm in diameter, not otherwise demonstrated to be artifacts by comparison with coregistered CT, recognizable as discrete foci

of increased 18F-FDG uptake on maximum intensity projection images (MIP), and exhibiting a max SUV (SUVmax) greater than the SUVmax for the patient's background red marrow.

The volume of each lesion and its 3D margins were determined by incorporating all contiguous pixels with activity greater than 0.1 g/mL above that of the background marrow. Because of the considerable statistical variability inherent in the acquisition, reconstruction, and display of accumulations of radiopharmaceuticals in the clinical imaging setting, SUVs obtained from larger regions of interest (ROI) are more reproducible than single pixel determinations such as SUVmax. For this reason, we have chosen to quantify activity by calculating the SUVmax defined as the average SUVs, corrected for lean body mass, of the pixels in a sphere 1.2 cm in diameter (1 cc) centered to include the most intense pixel.

The total MTV for disease in each patient was defined as the sum of MTVs of all the individual focal lesions identified in the analysis. The TLG of each focal lesion was calculated by multiplying the MTV of that lesion with its corresponding mean SUV (TLG = SUVmean \times MTV). The global TLG of each patient was defined as the sum of the TLGs for all the focal lesions in the analysis.

Lesions will be identified by the software based on the thresholds set in the workflow that works on adaptive thresholding. MTV will be obtained by summing the metabolic volumes of all nodal and extranodal lesions (TMTV = Σ MTVL). All volumes of interest that are drawn by the automated computer system will be evaluated by the reader to delete those regions that are not deemed to be associated with tumor. The review computer system will automatically calculate all quantitative assessments (SUVmax, MTV, TLG) for each lesions at baseline, mid therapy (when available) and end of therapy (EOT). In addition, at EOT, we will calculate the percentage of change from baseline for each qPET parameter.

10 Study Calendar

10.1 Calendar of Events: Original Study Design (Cohort A)

| Study Parameters and Calendar | Within 28 ^a days of D1 | Nivolumab only, 1 st 6 weeks (Wks) | | | Nivolumab only, 2 nd 6 weeks (not all pts) | | | NIVO + ICE ^b 6 weeks (not all pts) | | End of Treatment ^l | Post AHCT f/u |
|--|-----------------------------------|---|---------------------|---------------------|---|---------------------|---------------------|---|---------------------|-------------------------------|----------------|
| | | Wk1 D1 (± 3 day) | Wk3 D1 (± 3 day) | Wk5 D1 (± 3 day) | Wk1 D1 (± 3 day) | Wk3 D1 (± 3 day) | Wk5 D1 (± 3 day) | Wk1 D1 (± 3 day) | Wk4 D1 (± 3 day) | | |
| Nivolumab | | X | X | X | X | X | X | X | X | | |
| Ifosfamide ^c | | | | | | | | X | X | | |
| Carboplatin ^d | | | | | | | | X | X | | |
| Etoposide ^e | | | | | | | | X | X | | |
| Informed consent | X | | | | | | | | | | |
| Demographics | X | | | | | | | | | | |
| Medical history | X | | | | | | | | | | X |
| Concurrent meds | X | X | X | X | X | X | X | X | X | | |
| Physical exam | X | X | X | X | X | X | X | X | X | | X |
| Vital signs | X | X | X | X | X | X | X | X | X | | |
| Height | X | | | | | | | X | | | |
| Weight | X | X | X | X | X | X | X | X | X | | |
| Performance Status | X | X | X | X | X | X | X | X | X | | X |
| CBC w/diff, plts [†] | X | X | X | X | X | X | X | X | X | | |
| Serum chemistry* [†] | X | X | X | X | X | X | X | X | X | | |
| PT/PTT/INR [†] | X | X | X | X | X | X | X | X | X | | |
| TSH, T3, T4 [†] | X | X | X | X | X | X | X | X | X | | |
| EKG (as indicated) [†] | X | | | | | | | | | | |
| PFTs | X | | | | | | | | | | |
| Adverse event evaluation | | X | X | X | X | X | X | X | X | X | X ^m |
| Tumor measurements | X ^k | | | X ^k | | | X ^k | | X ^k | | |
| Radiologic evaluation ^f | X ^a | | | X ^f | | | X ^f | | X ^f | | |
| Tumor Biopsy ^g | X | | | X ^h | | | | | | | X ⁱ |
| B-HCG [†] | X | X ^{**} | | | | | | | | | |
| Research blood collection ^j | | X ^j | X ^j | X ^j | | | | X ^j | X ^j | | |
| Survival | | | | | | | | | | | X ⁿ |

^a Except for screening PET/CT, which can occur within 35 days of D1.

^b Filgrastim 5 mcg/kg given on days 5 to 12

^c 5 g/m² with equivalent dose of Mesna given over 24 hours by continuous infusion on day 2

^d area under the curve (AUC) of 5 with a maximum of 750 mg day 2

^e 100 mg/m²/day on days 1 to 3

^f PET-CT scans will be performed at end of weeks 6, 12, and 18. Once PET-CT is negative, it does not need to be performed again. Instead, a diagnostic quality CT of the neck, chest, abdomen, and pelvis will be performed.

^g Each subject will have either a fresh core or excisional biopsy of a tumor lesion prior to starting study therapy or will have available archival tissue from a biopsy that was performed after induction therapy.

^h Tumor biopsy (if safe and accessible) must be performed after the first CT/PET response assessment (and only in patients who did not reach CR). For patients (with PR) who are going to a second 6-week treatment with single-agent NIVO, biopsy may be performed at any time after the first CT/PET scan (but before any NIVO+ICE treatment). For patients (with SD or PD at first CT/PET) who are instead going to a 6-week treatment with NIVO+ICE, biopsy must be performed before starting NIVO+ICE.

ⁱ If feasible, all subjects will undergo biopsy of tumor lesion at the time of disease progression or relapse.

^j On Day 1 of Wks 1, 3, 5 of nivolumab, on Day 1 of Wks 1 and 4 of NIVO + ICE, and on last day of Wk 6 (C2D21) of NIVO + ICE or any day post-C2D21, but must be prior to AHCT.

^k Tumor measurements will be performed at the same time points indicated for PET-CT scans in footnote f.

^l Includes all patients, regardless of reason for end of protocol therapy; refer to [Section 5.5](#) for follow-up.

^m For patients who receive AHCT

ⁿ Refer to [Section 5.5](#) for post-AHCT survival assessments.

*Serum chemistry includes comprehensive metabolic profile: sodium, potassium, chloride, carbon dioxide, glucose, blood urea nitrogen, creatinine, AST, ALT, Alkaline phosphate, total bilirubin, calcium, albumin, total protein, magnesium, phosphate

** Women of childbearing potential must have a negative serum or urine pregnancy test (minimum sensitivity 25 IU/L or equivalent units of HCG) within 24 hours prior to the start of nivolumab.

† Must be performed within 10 days of treatment initiation.

10.2 Calendar of Events: New Design (Cohort B)

| Study Parameters and Calendar | Within 28 ^a days of D1 | Cycle 1 (14 days) | | Cycle 2+ (21 days) | | End of Treatment ¹ | Post AHCT f/u |
|--|-----------------------------------|-------------------|-----------------------|-----------------------|------------------------------------|-------------------------------|----------------|
| | | D1 (\pm 3 day) | C2, D1 (\pm 3 day) | C3, D1 (\pm 3 day) | C4, D1 ^m (\pm 3 day) | | |
| Nivolumab | | X | X | X | (X) | | |
| Ifosfamide ^c | | | X | X | (X) | | |
| Carboplatin ^d | | | X | X | (X) | | |
| Etoposide ^e | | | X | X | (X) | | |
| Informed consent | X | | | | | | |
| Demographics | X | | | | | | |
| Medical history | X | | | | | X | |
| Concurrent meds | X | X | X | X | (X) | X | |
| Physical exam | X | X | X | X | (X) | X | |
| Vital signs | X | X | X | X | (X) | X | |
| Height | X | | X | | | | |
| Weight | X | X | X | X | (X) | X | |
| Performance Status | X | X | X | X | (X) | X | |
| CBC w/diff, plts ^f | X | X | X | X | (X) | X | |
| Serum chemistry* [†] | X | X | X | X | (X) | X | |
| PT/PTT/INR [†] | X | X | X | X | (X) | X | |
| TSH, T3, T4 [†] | X | X | X | X | (X) | X | |
| EKG (as indicated) [†] | X | | | | | | |
| PFTs | X | | | | | | |
| Adverse event evaluation | | X | X | X | (X) | X | X ⁿ |
| Tumor measurements | X ^k | | | X ^k | | | |
| Radiologic evaluation ^f | X ^a | | | X ^f | (X) | | |
| Tumor Biopsy ^g | X | | | | | (X ⁱ) | |
| B-HCG [†] | X | X ^{**} | | | | | |
| Research blood collection ^j | | X ^j | X ^j | X ^j | | | |
| Survival | | | | | | | X ^o |

^a Except for screening PET/CT, which can occur within 35 days of D1.

^b Filgrastim 5 mcg/kg given on days 5 to 12

^c 5 g/m² with equivalent dose of Mesna given over 24 hours by continuous infusion on day 2 (inpatient schedule) or 1670 mg/m² with Mesna on Days 1-3 (outpatient schedule).

^darea under the curve (AUC) of 5 with a maximum of 750 mg day 2

^e 100 mg/m²/day on days 1 to 3

^f PET-CT scans will be performed at end of week 8. Once PET-CT is negative, it does not need to be performed again. Instead, a diagnostic quality CT of the neck, chest, abdomen, and pelvis will be performed.

^g Each subject will have either a fresh core or excisional biopsy of a tumor lesion prior to starting study therapy or will have available archival tissue from a biopsy that was performed after induction therapy.

ⁱIf feasible, all subjects will undergo biopsy of tumor lesion at the time of disease progression or relapse.

^jOn C1D1, C2D1, C3D1 or any day post-C3D21, but must be prior to AHCT.

^k Tumor measurements will be performed at the same time points indicated for PET-CT scans in footnote f.

^l Includes all patients, regardless of reason for end of protocol therapy; refer to [Section 5.5](#) for follow-up.

^m Optional cycle of NIVO +ICE at the investigator's discretion. PET/CT after Cycle 3, see footnote f.

ⁿ For patients who receive AHCT

^o Refer to [Section 5.5](#) for post-AHCT survival assessments.

^{*}Serum chemistry includes comprehensive metabolic profile: sodium, potassium, chloride, carbon dioxide, glucose, blood urea nitrogen, creatinine, AST, ALT, Alkaline phosphate, total bilirubin, calcium, albumin, total protein, magnesium, phosphate

^{**} Women of childbearing potential must have a negative serum or urine pregnancy test (minimum sensitivity 25 IU/L or equivalent units of HCG) within 24 hours prior to the start of nivolumab.

[†] Must be performed within 10 days of treatment initiation

11 Endpoint Evaluation Criteria/Measurement of Effect

11.1 Definitions

Evaluable for toxicity: All participants will be evaluable for toxicity from the time of their first treatment with nivolumab.

Evaluable for objective response: Only those participants who have measurable disease present at baseline, have received at least 4 weeks of therapy, and have had their disease re-evaluated will be considered evaluable for response. These participants will have their response classified according to the definitions stated below.

Duration of overall response: The duration of overall response is measured from the time measurement criteria are met for CR or PR, per 2014 Lugano Criteria,¹⁶ (whichever is first recorded) until the first date that relapsed or progressive disease is objectively documented.

Duration of overall CR: The duration of overall CR is measured from the time measurement criteria are first met for CR until the first date that progressive disease is objectively documented.

Duration of stable disease: Stable disease is measured from the start of the treatment until the criteria for progression are met, per 2014 Lugano Criteria,¹⁶ taking as reference the smallest measurements recorded since the treatment started, including the baseline measurements.

Overall Survival (OS): OS is defined as the duration of time from start of treatment to time of death (due to any cause).

Progression-Free Survival (PFS): PFS is defined as the duration of time from start of treatment to time of progression or death, whichever occurs first.

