Original Cohort: The *primary study endpoint* is complete response (CR) rate at the time of AHCT and is based on the Lugano Criteria.¹⁶ The primary endpoint for the patient *safety monitoring* segment of the study is toxicity. Toxicity will be scored using the NCI CTCAE v4.03 Scale. Unacceptable toxicity in a given patient is defined as any non-hematologic or hematological grade 3/4 toxicity that does not resolve to a grade 1/2 within 14 days per NCI CTCAE v4.03 toxicity criteria and is considered at least possibly related to nivolumab and/or ICE, or any other regimen-related cause of death.

New Cohort (B): The first primary endpoint is unacceptable toxicity. Toxicity will be scored using the NCI CTCAE v4.03 Scale. Unacceptable toxicity in a given patient is defined as any non-hematologic or hematological grade 3/4 toxicity that does not resolve to a grade 1/2 within 14 days per NCI CTCAE v4.03 toxicity criteria and is considered at least possibly related to nivolumab and/or ICE, or any other regimen-related cause of death. **Updated Apr 27, 2021:** The phase 2 portion will evaluate the anti-lymphoma activity of the two-agent combination as assessed by CR rate using Lugano criteria, in patients with high-risk HL as the second primary endpoint.

Sample Size:

Original Cohort (A): Assuming 1) the nivolumab 240 mg flat dose and ICE doses are well tolerated and 2) the study does not close for futility, 43 evaluable (received at least one cycle of treatment) patients will be enrolled on the phase II portion of the study. Expected accrual for safety monitoring segment: n=6.

New Cohort (B): We plan to enroll and treat 18 eligible patients. With 18 patients, we can estimate the proportion of patients experiencing unacceptable adverse events with sufficient precision (standard error ≤ 0.12 , half width ≤ 0.23). **Expanded Sample Size (Anti-Lymphoma Activity):** The Cohort B phase 2

portion is expected to enroll and treat a minimum of 19 and a maximum of 35 patients at the Cohort B schedule.

Estimated Duration of the Study

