7.2 Dose Delay Criteria for NIVO + ICE

Dose delays for NIVO + ICE are allowed under the following criteria:

- Hematological toxicity: Platelets $\leq 75,000$, Hemoglobin ≤ 8.5 , ANC $\leq 1,500$
- Non-hematological toxicity: All drug-related grade 3/4 AEs. These AEs need to resolve to grade 2 or lower before NIVO + ICE is given.

A delay of up to 14 days is allowed. After 14 days of delay, patients must be taken off the trial.

Filgrastim/packed red blood cells/platelet transfusions are allowed during this period, even during DLT assessment, as ICE therapy itself is supported by these transfusions.

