are in CR at this time, they will go directly to AHCT. For patients not in CR after 12 weeks of nivolumab, they will receive NIVO + ICE (combination of nivolumab plus ICE) x 6 weeks. Patients who only achieve SD after 6 weeks of single agent nivolumab can either receive an additional 6 weeks of single agent nivolumab, or receive a combination of nivolumab plus ICE for 6 weeks. The decision to go either way will be at the physician/investigator's discretion on a case-by-case basis. The rationale is that in patients with a radiographic response of SD who are clinically doing well, an immune response or tumor flares could be masking an actual PR or CR. For patients who only achieve PD after 6 weeks of single agent nivolumab, they will directly move onto the NIVO + ICE portion.

Study Design Rationale: This multicenter, single-arm, phase II trial is designed to evaluate the anti-lymphoma activity of the NICE 2nd-line regimen, in patients with relapsed or primary refractory HL post induction therapy. Activity will be assessed by CR rate prior to AHCT. Recent studies evaluating NIVO, an anti-PD-1 monoclonal antibody show efficacy in relapsed/refractory HL. In a phase I trial, NIVO was shown to have an ORR of 87% with a CR rate of 17%⁷. This response rate was recently confirmed in a phase II trial¹¹, and the drug received accelerated FDA approval for HL after failure of AHCT and BV treatment. In the Moskowitz study of PET imaging normalization prior to AHCT, 60% of patients who received 2nd-line ICE or augmented ICE achieved CR prior to AHCT¹². The MSKCC trial, which used augmented ICE, accrued 46 patients in 2 years, of whom 44 proceeded to AHCT, with 34 in CR (74%)¹³. In our study of PET-adapted BV ± chemotherapy prior to AHCT, 65% of enrolled/treated patients attained a CR pre-transplant¹⁴. Based on these data, a CR rate of 70% prior to AHCT will be considered promising, qualifying the regimen worthy of further investigation.

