The phase 2 portion will implement a Simon two-stage minimax design^{15,87} to evaluate the anti-lymphoma activity of the two-agent combination as assessed by CR rate, in patients with high-risk HL. The Cohort B phase 2 portion is expected to enroll and treat a minimum of 19 and a maximum of 35 patients at the Cohort B schedule. The sample size is based on the desire to discriminate a promising CR rate of 74% from a disappointing response rate of 50%³ using a type I error rate of 0.05 and power of 90%. At stage 1, 19 patients will be entered on the study. Note: The n=13 patients treated thus far as part of the safety evaluation portion of the study will count toward the 35 patients required; given this, we expect to enroll only 22 new patients on the Cohort B phase 2 trial. If ≤ 9 complete responses are seen, the study will be terminated. If at least 10 patients achieve CR, the trial will continue to the second stage. At stage 2, 16 additional patients will be entered. At the end of stage 2, if 23 or more patients experience complete response, the combination will be considered worthy of further study. If ≤ 22 patients achieve a complete response then no further investigation of the combination is warranted.

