12.4 Statistical Analysis Plan

In general, data will be summarized by using counts and percents for discrete parameters, and by descriptive statistics (number of observations, mean, standard deviation, median, minimum and maximum) for continuous parameters. Response rates will be calculated as the percent of evaluable patients that have confirmed CR by radiographic response including CT and/or PET scans; 95% Clopper Pearson confidence limits will be calculated for this estimate. Toxicity information recorded will include the type, severity, and the probable association with the study regimen. Tables will be constructed to summarize the observed incidence by severity and type of toxicity. Baseline information (e.g., the extent of prior therapy) and demographic information will be presented as well to describe the patients treated in this study. Time to response and survival endpoints will be estimated using the product-limit method of Kaplan and Meier. The

cumulative incidence of relapse/progression and non-relapse mortality will be calculated as competing risks using the method of Gooley et al¹⁷.

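### Section 12.4 divides the CR rate by evaluable patients; in Cohort B this drops treated patients who leave before 4 weeks or without response imaging, and in Cohort A the meaning of evaluable is in conflict.

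*Combined protocol and SAP*

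**What the plan says.** Section 11.1 (Definitions) narrows the response-evaluable set: "Only those participants who have measurable disease present at baseline, have received at least 4 weeks of therapy, and have had their disease re-evaluated" qualify. Section 12.4 (Statistical Analysis Plan) then sets the denominator: "Response rates will be calculated as the percent of evaluable patients that have confirmed CR by radiographic response including CT and/or PET scans", with 95% Clopper-Pearson limits. The Statistical Considerations part of the synopsis repeats this. Neither place says how to count a treated patient who has no response assessment.

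Two other places describe the patients differently:

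- For Cohort B, section 12.1.1 states the Simon design in terms of treated patients: "The Cohort B phase 2 portion is expected to enroll and treat a minimum of 19 and a maximum of 35 patients". Success is 23 or more CRs.
- For Cohort A, the Sample Size part of the synopsis attaches its own meaning to the word: "43 evaluable (received at least one cycle of treatment) patients will be enrolled on the phase II portion of the study".

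The Cohort B calendar (section 10.2) sets the response scan late: "PET-CT scans will be performed at end of week 8". It marks no radiology at the End of Treatment visit. Section 7.2 ends participation after a prolonged NIVO+ICE delay: "After 14 days of delay, patients must be taken off the trial".

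**The concern.** A patient with no re-evaluation cannot be recorded as a CR. Removing such patients takes only failures out of the denominator, so any error runs in one direction. Patients may leave early because of toxicity, clinical deterioration, death or withdrawal, and most of these are outcomes that the CR rate before transplant should reflect.

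The CR rate is the primary efficacy endpoint of both cohorts. Cohort B is meant to show whether that rate is promising against historical data in high-risk patients. If the published rate rests on fewer patients than the Simon rule, the estimate and the go/no-go decision describe different groups.

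**Working it through.** **1. The plan's own designs.** Let n1 and n be the stage 1 and total sample sizes, and let the design stop at r1 or fewer CRs in stage 1 and fail at r or fewer overall. For true CR rate p, the probability of success is the sum over x from r1+1 to n1 of P(X1 = x) × P(X2 ≥ r+1−x), where X1 ~ Bin(n1, p) and X2 ~ Bin(n−n1, p).

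| Cohort | r1/n1 | r/n | Null, target CR rate | Type I error | Power |
|---|---|---|---|---|---|
| A | 8/15 | 26/43 | 50%, 70% | 0.0499 | 0.804 |
| B | 9/19 | 22/35 | 50%, 74% | 0.0444 | 0.900 |

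Both match the stated 0.05 with 80% and 90% power. They hold when every entered patient counts and an unassessed patient is a non-CR.

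**2. Who can fall out in Cohort B.** There are two routes:

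- Leaving before 4 weeks of therapy, for example during the 14-day nivolumab cycle or soon after the first NIVO+ICE dose.
- Leaving after 4 weeks with no response imaging. Cycle 1 lasts 14 days and Cycle 2 lasts 21, so Cycle 3 is due at day 14 + 21 + 1 = 36. A 14-day delay that does not resolve ends participation at about day 36 + 14 = 50. The end of week 8 is day 56. The patient has had more than 4 weeks of therapy, but the only scheduled response scan has not yet been reached.

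**3. How many are exposed.** Section 2.5 reports 13 Cohort B patients treated, all in CR, and section 12.1.1 counts them toward the 35. At most 35 − 13 = 22 patients can be affected. The documents give no expected number of early exits.

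**4. Effect on the reported rate.** Excluding k of n patients with the CR count fixed multiplies the rate by n/(n−k). For n = 35 this is 35/34 = 1.029 for k = 1 and 35/33 = 1.061 for k = 2. The values of k are illustrative. The 29 CRs in the second row assume 13 observed plus the 74% target in the other 22: 13 + 0.74 × 22 = 29.3. Brackets give 95% Clopper-Pearson limits.

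| Case | No exclusion | One excluded | Two excluded |
|---|---|---|---|
| B, pass mark | 23/35 = 65.7% (47.8–80.9) | 23/34 = 67.6% (49.5–82.6) | 23/33 = 69.7% (51.3–84.4) |
| B, 29 CRs | 29/35 = 82.9% (66.4–93.4) | 29/34 = 85.3% (68.9–95.0) | 29/33 = 87.9% (71.8–96.6) |
| A, pass mark | 27/43 = 62.8% (46.7–77.0) | 27/42 = 64.3% (48.0–78.4) | 27/41 = 65.9% (49.4–79.9) |

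The Cohort A row applies only if 11.1, and not the synopsis definition, governs 12.4.

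**5. Effect on the decision.** The success rules are counts, 27 CRs in Cohort A and 23 in Cohort B. Dropping a non-CR from a percentage does not change a count, so the results in step 1 stand.

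**The case against.** **Cohort A is not a settled exclusion.** The one-cycle definition in the synopsis keeps most early leavers in. This stands: for Cohort A the finding is a conflict between two definitions. The synopsis gives no such alternative for Cohort B.

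**Progression is often already handled.** Progression shown on imaging after 4 weeks is itself a re-evaluation, so that patient is an evaluable non-CR. In Cohort A, progression at week 6 leads to NIVO+ICE and a later scan. This stands too, and it limits the gap to exits before 4 weeks or exits with no imaging.

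**The day-50 route is a chain of conditions.** It needs a full 14-day delay and no unscheduled scan, about six days before the planned one. Section 7.5 also says tumor assessments continue when dosing is interrupted. That text sits under exceptions for interruptions longer than 6 weeks, while 7.2 is specific to NIVO+ICE. The route is weakened but remains possible, since the calendar requires no scan on leaving.

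**The pass-mark example is pessimistic.** Reaching only 23 CRs means 10 of the next 22 (45%), after 13 of 13. The 29-CR row is the more plausible one, and there both lower limits exceed 50%.

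**Two stronger readings are tempting but unsupported.** A reader might infer that the false-positive rate of the trial is inflated. That would need excluded patients to be replaced, which no section states. A reader might also infer that both cohorts are compared with all-patient benchmarks. The figures in 12.1.1 that show this belong to the Cohort A rationale: one study is reported as "65% of enrolled/treated patients attained a CR pre-transplant", and another prints 34 CRs as 74%, which fits 34/46 accrued (73.9%) and not 34/44 transplanted (77.3%). For the Cohort B comparators in section 2.5, the documents do not say which denominator was used.

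**Conclusion.** The concern holds as a one-way bias in the reported primary CR rate for Cohort B, and as an unresolved definition for Cohort A. With two exclusions the Cohort B estimate rises by 4 to 5 percentage points. Only in the pass-mark case does the lower limit cross the 50% null. The direction follows from the definitions alone. The size rests on assumed exclusion counts and, in the 29-CR case, on the 74% target rate in the remaining patients. If everyone is assessed after at least 4 weeks, nothing changes.

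This should be corrected, but it is a matter of estimation and reporting: the go/no-go counts and the error rates are sound as written. The benchmark mismatch is a Cohort A point only.

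**What to change.** In section 12.4, define the primary CR-rate denominator in each cohort as all eligible patients who received any study treatment. Count any of them without a post-treatment response assessment as non-CR, whatever the reason for stopping. Keep the 11.1 evaluable set as a sensitivity analysis, and report the number of treated patients outside it with the reason for each. Align the use of the word evaluable in the synopsis with this.

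The cost is a few sentences. Treatment, response and off-treatment forms are already collected under the data submission schedule, so no new data or procedures are needed. Cohort B enrolls only after Cohort A is completed, so for Cohort A the change affects analysis and reporting only. The downside is a reported rate that may be slightly lower.
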